8.3.6 SARS NOT REQUIRING IMMEDIATE REPORTING

The most recent Investigator Brochure (IB) for the IMPs being used in this trial will be circulated to participating centres by the UoSCTU and is to be stored in the local site file.

Side effects and toxicities that are expected are listed in the IB do not require immediate reporting in this trial, unless they are of an unexpected severity.

Death as a result of disease progression and other events that are primary or secondary outcome measures are also not considered to be SAEs.

SAEs of the above types should be recorded on the SAE/SUSAR form provided and this should be forwarded to the UoSCTU in a timely manner.

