2.2 SECONDARY ENDPOINTS

2.2.1 CML:

- 1) Molecular response of BCR-ABL (major response or CMR, as defined in Section 9.6).
- 2) Molecular response of WT1 (major or minor response or CMR, as defined in Section 9.6).
- 3) Time to disease progression. Disease progression for CML patients is defined as a loss in complete haematological response, where at least one factor falls out of the following ranges (81):
 - WBC < 10×10^9 /L
 - Basophils < 5%
 - No myelocytes, promyelocytes, myeloblasts in the differential
 - Platelet count < 450 x 10^9 /L

- Spleen nonpalpable
- 4) Time to next treatment. A next treatment is defined as the first drug taken during the course of the study with an indication to treat CML.
- 5) Duration of molecular response:
 - a. Measured from the beginning of tyrosine kinase inhibitor treatment.
 - b. Measured from the time of obtaining informed consent
- 6) Overall survival.
- 7) Toxicity assessed according to NCI CTCAE v4.0.
- 8) Pain assessment immediately after vaccination
- 9) Pain assessment at 48 hrs post vaccination

2.2.2 AML:

- 1) 2 year overall survival
- 2) 2 year progression free survival.
- 3) Overall survival.
- 4) Molecular response of WT1 (major or minor response or CMR, as defined in section 9.6).
- 5) Toxicity assessed according to NCI CTCAE v4.0
- 6) Pain assessment immediately after vaccination
- 7) Pain assessment at 48 hrs post vaccination

2.2.3 HLA A2 positive patients only (CML and AML):

- 1) Immune response to WT1-epitope specific T cells in blood and/or bone marrow, using validated assays by ELISPOT and/or ICS and tetramer staining. A positive response using the validated assays by ELISPOT is defined in Section 9.6.
- 2) Number of WT1 specific T-cells after peptide challenge to the skin (wherever assessment is feasible).
- 3) Immune response to DOM, using validated assays by ELISA.
- 4) Immune response to DOM specific T cells, using validated assays by ELISPOT.
- 5) Number of humoral responses (B-cells) to the vaccine components, by ELISA.

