8 PHARMACOVIGILANCE

8.1 **DEFINITIONS**

The Medicines for Human Use (Clinical Trials) Regulations 2004, as amended, provides the following definitions relating to adverse events in trials with an investigational medicinal product:

Adverse Event (AE): any untoward medical occurrence in a patient or clinical trial subject administered a medicinal product and which does not necessarily have a causal relationship with this treatment. *An AE can therefore be any unfavourable and unintended sign (including an abnormal laboratory finding), symptom, or disease temporally associated with the use of an investigational medicinal product (IMP), whether or not considered related to the IMP.*

Adverse Reaction (AR): all untoward and unintended responses to an IMP related to any dose administered.

All AEs judged by either the reporting investigator or the sponsor as having reasonable causal relationship to a medicinal product qualify as adverse reactions. The expression reasonable causal relationship means to convey in general that there is evidence or argument to suggest a causal relationship.

Unexpected Adverse Reaction: an AR, the nature or severity of which is not consistent with the applicable product information (e.g. investigator's brochure (IB) for an unapproved investigational product).

When the outcome of the adverse reaction is not consistent with the applicable product information this adverse reaction should be considered as unexpected. Side effects documented in the IB which occur in a more severe form than anticipated are also considered to be unexpected.

Serious Adverse Event (SAE) or Serious Adverse Reaction (SAR): any untoward medical occurrence or effect that at any dose:

- Results in death
- Is life-threatening refers to an event in which the subject was at risk of death at the time of the event; it does not refer to an event which hypothetically might have caused death if it were more severe
- Requires hospitalisation, or prolongation of existing inpatients' hospitalisation
- Results in persistent or significant disability or incapacity
- Is a congenital anomaly or birth defect

Medical judgement should be exercised in deciding whether an AE/AR is serious in other situations. Important AE/ARs that are not immediately life-threatening or do not result in death or hospitalisation but may jeopardise the subject or may require intervention to prevent one of the other outcomes listed in the definition above, should also be considered serious.

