8.3.2 NON SERIOUS AR/AES

All such toxicities, whether expected or not, should be recorded in the toxicity section of the relevant case report form and sent to the UoSCTU within one month of the form being due.

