8.3.3 SERIOUS ADVERSE EVENTS AND REACTIONS

Fatal or life threatening SAEs and SUSARs should be reported within 24 hours of the local site becoming aware of the event. The SAE/SUSAR form asks for nature of event, date of onset, severity, corrective therapies given, outcome and causality (i.e. unrelated, unlikely, possible, probably, definitely). The responsible investigator should assign the causality and expectedness of the event with reference to the current IMP IB and use the event terms and grades given in the NCI CTCAE v4.0. Additional information should be provided as soon as possible if the event/reaction has not resolved at the time of reporting.

Relapse and death due to CML or AML, and hospitalisations for elective treatment of a pre-existing condition do not need reporting as SAEs.

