10.2 ANALYSIS PLAN

Molecular Analysis

The analyses on molecular response will be performed on all patients with molecular data at a minimum of 2 post-baseline time points (HLA A2 positive patients must also have received at least 1 dose of the vaccine).

Immunological Analysis

To be evaluable for immunological response, positive HLA A2 patients must receive at least 1 dose of the vaccine and the immunological testing must be available until at least week 8 post first dose.

Safety Analysis

For safety analyses, all patients with positive HLA A2 status who received at least one study drug administration will be evaluable for toxicity. All controls will be included in the safety analyses, where relevant.

Other Analysis

For all other analyses, an intention to treat principle will be used.

10.2.1 ANALYSIS FOR CML PATIENTS ONLY:

Primary:

The primary endpoint is molecular response of BCR-ABL (major or minor response or CMR). For the purpose of analysis, response (as defined by section 9.6) will be measured at weeks 4, 8, 12, 16, 20, 32 and 11, 17 and 23 months. Fisher's exact test will be used to compare differences in proportions of molecular response in CML patients versus controls.

Secondary:

The primary analysis will be repeated for major response or CMR of BCR-ABL.

The analysis methods used for BCR-ABL will be repeated for WT1.

Progression free survival, duration of response and overall survival (as defined in Section 2.2) will be estimated using the method of Kaplan and Meier for each group. Survival estimates will be presented with 90% confidence intervals. These endpoints will also be compared between the CML patients and controls using log-rank tests.

Progression free survival for CML patients is defined in Section 2.2 and is measured as the time from date of consent to the study to date of progression or death from any cause. Alive patients who are progression free will be censored at their date of last follow up. Similar analysis will be performed for overall survival and duration of response.

Toxicity will be collected and evaluated according to the NCI CTC toxicity scale (v4.0) and compared between the vaccinated and control groups by Fisher's exact test.

10.2.2 ANALYSIS FOR AML PATIENTS ONLY:

Primary:

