The primary endpoint is time to disease progression measured as the time from date of consent to the study to date of progression or death from any cause (progression is defined as disease relapse). Alive patients who are progression free will be censored at their date of last follow up. Progression free survival will be estimated using the method of Kaplan and Meier for each group. Survival estimates will be presented with 90% confidence intervals. A log rank test will be computed to compare AML patients and their controls.

Secondary:

The primary analysis will be repeated for survival time.

A secondary endpoint is molecular response of WT1 (major or minor response or CMR). For the purpose of analysis, response (as defined in section 9.6) will be measured at weeks 4, 8, 12, 16, 20, 32 and 11, 17 and 23 months. Proportions of responders in the vaccinated group will be compared with the control group using Fisher's exact test for the CML and AML groups. This analysis will be repeated for major molecular response or CMR of WT1.

Toxicity will be collected and evaluated according to the NCI CTC toxicity scale (v4.0) and compared between the vaccinated and control groups by Fisher's exact test.

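### Protocol 8.3.6 takes every outcome-measure event out of SAE status, so as written non-leukaemia deaths and serious toxicities fall outside the 24-hour rule set by 8.1, 8.3.3 and 8.3.4

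*Protocol*

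**What the plan says.** Section 8.3.6 deals with serious reactions that need no immediate report. It first exempts expected reactions listed in the IB, unless their severity is unexpected. It then adds: "Death as a result of disease progression and other events that are primary or secondary outcome measures are also not considered to be SAEs". The sentence after that reads "SAEs of the above types should be recorded on the SAE/SUSAR form provided" and asks for timely forwarding to the trials unit, with no number of hours or days.

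Three other sections set the general rule:
- 8.1 lists a fatal outcome as a criterion of seriousness.
- 8.3.3 requires fatal or life-threatening SAEs within 24 hours. Its own exemption is narrow: "Relapse and death due to CML or AML, and hospitalisations for elective treatment of a pre-existing condition do not need reporting as SAEs".
- 8.3.4 requires a form within 24 hours for every SAE and SUSAR.

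The outcome measures are in 2.1, 2.2 and 10.2. The AML primary analysis runs "to date of progression or death from any cause (progression is defined as disease relapse"). CML progression free survival "is measured as the time from date of consent to the study to date of progression or death from any cause". Overall survival is a secondary endpoint in both diseases, and AML also has "2 year overall survival". Toxicity graded by CTCAE is a secondary endpoint in both.

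**The concern.** The first half of the 8.3.6 clause is the usual exemption for deaths from the disease under study. The second half has no limit. In this trial the outcome measures include all deaths and all graded toxicity, so an exemption for outcome-measure events covers most of what SAE reporting exists to catch.

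The sponsor's own causality judgement is what is at stake. Section 8.1 says: "All AEs judged by either the reporting investigator or the sponsor as having reasonable causal relationship to a medicinal product qualify as adverse reactions". The sponsor can make that judgement only once it has the event. Section 7.1.8 names possible cytopenia and immune-related renal or cardiac toxicity, and a death with such a component could be attributed locally to something else. Section 4.5 ties stopping to life-threatening vaccination-related toxicity in more than one patient, so the timing of a single reclassified event can matter.

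**Working it through.** No formula applies, because the protocol gives no figure for this rule. The check sets the sections side by side for each kind of event inside the reporting window of 8.3.5, which runs to four weeks after the last study drug.

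| Event | Under 8.1, 8.3.3 and 8.3.4 | Under 8.3.6 |
|---|---|---|
| Death not due to leukaemia | SAE, 24 hours | Not an SAE (outcome measure), then SAE form with no deadline |
| Serious toxicity not listed in the IB | SAE, 24 hours | Not an SAE (toxicity is an outcome measure), then SAE form with no deadline |
| Relapse or leukaemia death | No SAE report (8.3.3) | Not an SAE, but SAE form with no deadline |
| Serious expected reaction listed in the IB | SAE, 24 hours (8.3.4 covers all SAEs) | No immediate report, SAE form with no deadline |

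Step 1: is a non-leukaemia death an outcome-measure event? Yes. It is an event in the AML primary analysis (10.2.2), in CML progression free survival (10.2.1) and in overall survival (2.2.1, 2.2.2).

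Step 2: is a serious toxicity one? Yes, through CTCAE toxicity in 2.2.1 and 2.2.2.

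Step 3: does 8.3.3 already exempt these? No. It exempts only relapse, death due to CML or AML, and elective admissions.

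Step 4: is 8.3.6 consistent within itself? Not on the natural reading. It says the outcome events are not SAEs, and its next sentence refers to SAEs of the types just described. Only if that sentence means the IB-listed reactions alone does the conflict go away.

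Step 5: who is affected? The 8.3.5 window is tied to study drug and controls receive none, so the conflict concerns vaccinated patients. At target size that is 32 CML + 39 AML = 71. With the 36 CML patients that 10.1.1 plans to recruit it is 36 + 39 = 75. Replacements under 3.1 would add to either figure.

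Step 6: what route remains? A reaction that the site suspects and finds both serious and unexpected is a SUSAR and keeps its 24-hour route under 8.3.3 and 8.3.4. The conflict is left with events that the site does not report as SUSARs, chiefly those it judges unrelated or unlikely to be related. For these the choice is 24 hours or an undated timely report.

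**The case against.** The best defence is that no one would read the clause this way. If outcome-measure events already included every death, naming progression deaths separately would be redundant. If they included toxicity, the rest of section 8 would have almost nothing to act on. The sensible reading is disease-outcome events, which matches 8.3.3. This is a fair account of the probable intent. But the text does not state it, and nothing ranks 8.3.3 above 8.3.6 when a site meets both.

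Safeguards also exist. Section 8.2 tells investigators to inform the trials unit when causality is in doubt. Section 12.1 has the Trial Management Group review safety listings every 2 to 3 months, alongside DMEC review. These soften the delay but do not settle which rule a site should follow.

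A reader might infer three stronger points, none of which the protocol supports:
- *Deaths could go unreported or be lost to analysis.* Section 9 has survival collected prospectively for all patients, and the last sentence of 8.3.6, read with the clause before it, still sends the event on the SAE form.
- *A non-leukaemia death could fall to the slow route "sent to the UoSCTU within one month of the form being due".* That is 8.3.2, which covers only non-serious toxicities, and no text sends a death there.
- *Fatal suspected reactions would be delayed.* Those that the site finds unexpected are SUSARs and keep the 24-hour route.

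The disagreement over relapse and leukaemia death is the lesser part. If the last sentence of 8.3.6 means only IB-listed reactions, the clash with 8.3.3 disappears. If it means more, the cost is some surplus forms.

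**Conclusion.** Section 8.3.6 is wrong as written and should be corrected. Its literal text removes non-leukaemia deaths and serious toxicities from SAE status, against 8.1, 8.3.3 and 8.3.4, and on the natural reading it gives relapse and leukaemia death a different route from 8.3.3.

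The practical size is modest. It amounts to inconsistent classification between sites and possibly later sponsor review of events in vaccinated patients within the 8.3.5 window that are not reported as SUSARs. The protocol gives no rate of non-leukaemia death or serious toxicity, so no event count can be given. Endpoints, sample size and analysis are unaffected.

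The conclusion assumes that sites apply 8.3.6 as worded. The part about relapse and leukaemia death also assumes that the final sentence of 8.3.6 covers both kinds of event named before it.

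**What to change.** Make five wording changes in one amendment:

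1. In 8.3.6, replace the outcome-measure clause with: *Relapse or progression of, and death due to, CML or AML are not SAEs.*
2. Add to 8.3.6: *Death from any other cause, and any other serious toxicity not listed as expected in the IB, within the 8.3.5 reporting period is an SAE and is reported within 24 hours.*
3. In the last sentence of 8.3.6, name the events it covers: *Serious expected reactions listed in the IB.*
4. In 8.3.4, add to the 24-hour rule: *except those listed in 8.3.6.* Without this, the IB-listed reactions still contradict it.
5. In 8.3.3 and 8.3.6, state one route in the same words for relapse, progression and leukaemia death, for example the CRF only.

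The cost is the amendment itself, with the GTAC and MHRA review that 11.3 requires, plus one 24-hour form for each such death or serious toxicity in a vaccinated patient. Sections 8.1, 8.3.3 and 8.3.4 already ask for that form. No visits or data items are added.

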8.3.7 PREGNANCY

If a subject or his/her partner becomes pregnant whilst taking part in the trial or during a stage where the foetus could have been exposed to an IMP, the investigator must ensure that the subject and the subject's healthcare professional are aware that follow up information is required on the outcome of the pregnancy. If the subject leaves the area, their new healthcare professional should also be informed.

9 ASSESSMENT AND FOLLOW-UP OF PATIENTS

It is intended that all patients will be followed on study for up to 36 months from date of informed consent. Date and type of subsequent treatments and survival data for all patients will be collected prospectively.

9.1 **PRE-TREATMENT EVALUATIONS**

The following investigations should be performed within 1 month of starting treatment. (It is anticipated that these investigations will be performed as standard clinical care; if they are not, consent must be obtained prior to any study related procedure/s):

- Bone Marrow aspirate for assessment of bone marrow cellularity and immunological evaluation (all patients except HLA A2 negative CML patients) and for disease evaluation (in AML) If a bone marrow sample is available within 1 month prior to recruitment in the study, a second bone marrow examination is not performed, unless clinically indicated.
- Chest X-Ray (HLA A2 positive patients only)
- ECG (HLA A2 positive patients only)
- Echocardiogram (HLA A2 positive patients only)

The following investigations/evaluations should be performed after consent and registration, and prior to starting treatment:

- HLA Status
- Demographic data
- Medical history
- Prior treatment malignancy
- Height and weight
- Physical examination
- WHO Performance status
- Vital Signs
- FBC and differential blood count, ESR
- Clotting
- Biochemistry
- CK test (HLA A2 positive patients only)
- Urine analysis (HLA A2 positive patients only)
- Syphilis, Hep B, Hep C, HIV
- Blood for immunological assays (80 ml of anticoagulated blood)
- qPCR for BCR-ABL and WT1 in CML, for WT1 in AML
- Leukapheresis for immunological studies (HLA A2 positive patients only)

- Autoimmune profile
- Concomitant diseases/treatments
- Adverse Events

Please also refer to the tabulated Schedule of Observations and Procedures (on pages 13-16).

9.2 VACCINE SHIPMENT TO THE PARTICIPATING TRIAL CENTRES

Vaccine will be shipped to sites around the time of activation. Stock levels should be monitored by sites and drug orders should be placed through the UoSCTU. It is advised that at least 7 days notice should be given.

The UoSCTU will place the drug order with [name], in Bristol, or his designated deputee who will then authorize and organise shipment of vaccines p.DOM-WT1-37 and p.DOM-WT1-126 on dry ice to the participating centre.

9.3 EVALUATIONS DURING AND AT THE END OF THE STUDY

HLA Status: Registratio	n
Visit 0: Baseline (once	
Visit 1: week 0	within 7 days of baseline visit
Visit 2: week 2	14 days after v1 +/- 3 days (Not done for HLA A2 negative patients)
Visit 3: week 4	14 days after v2 +/- 7 days
Visit 4: week 8	28 days after v3 +/- 7 days
Visit 5: week 10	14 days after v4 +/- 3 days (Not done for HLA A2 negative patients)
Visit 6: week 12	14 days after v5 +/- 7 days
Visit 7: week 16	28 days after v6 +/- 7 days
Visit 8: week 20	28 days after v7 +/- 7 days
Visit 9: week 22	14 days after v8 +/- 3 days
Visit 10: week 24-28	14-42 days after v9 +/- 14 days
Visit 11: week 32	56-28 days after v10 (depending on date of v10) +/- 14 days
Visit 12: week 34	14 days after v11 +/- 3 days
Visit 13:	11 months after baseline +/- 14 days
Visit 14:	14 months after baseline +/- 14 days
Visit 15:	17 months after baseline +/- 14 days
Visit 16:	14 days after visit 15 +/- 3 days
Visit 17:	20 months after baseline +/- 14 days
Visit 18:	23 months after baseline +/- 14 days
Visit 19:	24 months after baseline +/- 14 days
Visit 20:	27 months after baseline +/- 14 days
Visit 21:	30 months after baseline +/- 14 days
Visit 22:	33 months after baseline +/- 14 days
Visit 23:	36 months after baseline +/- 14 days
After Visit 23, month 3	6, follow-up outcomes should continue to be recorded.

If delays occur on vaccination visits, all subsequent visits will be slipped to keep the interval between vaccinations at 1 and 3 months, respectively. The day 14 post vaccination visits (v2, v5, v9 and v12) should be kept as close to 14 days as possible, allowed +/- 3 days.

Investigations required at each visit:

- FBC and differential blood count, ESR
- Biochemistry
- CK test (HLA A2 positive patients only)
- Urine analysis (HLA A2 positive patients only)

- Immunological monitoring*; 65 ml of anticoagulated blood (Lithium Heparin Tubes) and 5 mL clotted blood for serum will be taken for this purpose. (Blood should be taken prior to vaccine being administered).

Investigations required at visits 1, 2, 3, 4, 6, 7, 8, 11, 13, 14, 15, 17 and 18:

- Height and weight
- Physical examination
- WHO performance status
- Vital signs

HLA A2 positive patients only - Additional investigations required after each vaccination*(Visits 1, 3, 4, 6, 7, 8, 11, 13, 14, 15, 17 and 18):

- ECG
- Echocardiogram (if clinically indicated)
- Assessment of pain and discomfort of vaccination sites
- Additionally, patients will be observed for 2 hours post each vaccination at the trial site. If the absence of adverse events supports this, the TMG may decide to waive this requirement after 12 patients have completed the first 6 doses of vaccination.

*The first HLA A2 positive patient recruited at each site will be evaluated at 48 hours after her/his first vaccination, before additional doses can be given or before additional patients can be vaccinated at that site.

HLA A2 positive patients only - Additional investigation required Visit 6

- DTH assessment (to be carried out if wherever feasible)

HLA A2 positive patients only - Additional investigations required at Visit 7

- Autoimmune profile

HLA A2 positive patients only - Additional investigations required at Visit 10

- Bone marrow for immunological (CML and AML) and disease (AML) evaluation
- Leukapheresis
- Autoimmune profile
- DTH assessment (to be carried out if wherever feasible)

HLA A2 positive patients only - Additional investigations required at Visit 16

- Autoimmune profile

HLA A2 positive patients only - Additional investigations required at Visit 23

- Autoimmune profile

Please also refer to the tabulated Schedule of Observations and Procedures (on pages 13-16).

